**Retention measures of OUD treatment (Implementation Fidelity).**

**\*Retention in OUD treatment.** Clinic-level number of patients initiating§ OUD treatment during the period from randomization until two years after randomization as documented in the EHR, who also receive OUD treatment on 80% of days available after initiation, reported per 10,000 PC patients in the clinic in the two years post-randomization.

**Retention in OUD treatment for  $\geq 6$ -months** Clinic-level number of patients initiating§ OUD treatment during the period from randomization until two years after randomization as documented in the EHR, who remain on treatment for  $\geq 6$  months after initiation, reported per 10,000 PC patients in the clinic in the two years post-randomization.\*\*\*

**Discontinuation of OUD treatment.** Clinic-level number of patients initiating§ OUD treatment during the period from randomization until two years after randomization as documented in the EHR, who discontinue treatment (defined as a gap of 60+ days), reported per 10,000 PC patients in the clinic in the two years post-randomization.

§See definition of initiation above;

\*\*\*Excludes patients whose only eligible PC visit occurred in the last 6 months of the post-randomization period or who began OUD treatment in the last 6-months of the post-randomization period. Measures of retention above will also be estimated for all subjects regardless of new or on-going treatment and for subjects with on-going treatment.

**Number of buprenorphine prescribers (Implementation Fidelity).** Clinic-level number of buprenorphine prescribers† during the period from randomization until two years after randomization as documented in the EHR, who prescribe buprenorphine, reported per 10,000 PC patients in the clinic in the two years post-randomization.

Number of buprenorphine prescribers will also be reported per X total prescribers in the clinic in the two years post-randomization.

†Prescribers determined from medication orders in the electronic health records. Providers assigned to clinics based on number of visits with patients in the clinic pre-randomization.

**\*Naloxone prescribing (Implementation Fidelity).** Patient-level number of prescriptions of naloxone for overdose management in the period from randomization until two years after, among patients with an OUD diagnosis in the three years prior to randomization.

**OUD treatment duration (Implementation Fidelity).** Patient-level number of days of OUD treatment with buprenorphine and XR-NTX documented in the EHR during the period from randomization until two years after, among patients with an OUD diagnosis in the three years prior to randomization. This measure will be modeled as a categorical variable (0 days, 1-30 days, 31-90 days, 91-180 days,  $\geq 180$  days).

**Other Outcome Measures of Effectiveness**

**\*Urgent care or ED use\*\*.** Patient-level number of visits to urgent care or EDs during the period from randomization until two years after, among patients with an OUD diagnosis documented in the EHR in the 3 years prior to randomization. Urgent care and ED are combined into a single outcome to represent “emergency care”.

This measure will secondarily be modeled as a categorical variable (with cut-points based on the empirical distribution).

\*\* ED or Urgent Care visits that lead to hospitalization are classified as inpatient.

**\*Inpatient days hospitalized\*\*.** Patient-level number of days hospitalized during the period from randomization until two years after, among patients with an OUD diagnosis documented in the EHR in the three years prior to randomization.

**Any acute care.** Patient-level binary indicator for whether the patient had any acute care utilization during the period from randomization until two years after, among patients with an OUD diagnosis documented in the EHR in the three years prior to randomization.

**Number of hospitalizations \*\*.** Patient-level number of hospitalizations during the period from randomization until two years after, among patients with an OUD diagnosis documented in the EHR in the three years prior to randomization. This measure will be modeled as a categorical variable (with cut-points based on the empirical distribution).

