Opioid overdose* (Secondary patient outcome)	Proportion of patients with an ICD code for opioid overdose during follow-up (Note this is expected to be biased due to improved ascertainment in the PROUD clinics due to NCM follow-up with patients with OUDs).
HCV viral cure* (Secondary patient outcome)	Number of patients with HCV who have documented viral suppression among all with diagnosed chronic active HCV.
Additional Outcome Measures - Other Processes of Care	
New diagnosis or treatment of other substance use condition*	Number of patients who have a new diagnosis or treatment for another substance use condition (not diagnosed prior 2 years)

New diagnosis or treatment of mental health conditions*	Number of patients who have a new diagnosis or treatment for a mental health condition (not diagnosed prior 2 years)
Naloxone prescribing	Patient-level number of prescriptions of naloxone for overdose management in the period from randomization until two years after, among patients with an OUD diagnoses in the three years prior to randomization. Number of prescriptions of naloxone for OD management among patients with OUD diagnoses during follow up
HCV & HIV Screening or treatment*	Number of patients with new OUD diagnoses who have screening tests or treatment for HCV or HIV

~~*Not included in ClinicalTrials.gov since they are exploratory and not tested in Phase 1 therefore inadequate validation prior to the trial. *Measured in the 2 years after randomization using EHR data, reported per 10,000 PC patients in a clinic in the 3 years prior to randomization.~~

Rationale: Clarifications were noted to be needed when measures were prepared for ClinicalTrials.gov. We are updating additional outcome measures in Table 7 to align with our published ClinicalTrials.gov registration, as well as clarify clinic vs. patient-level measures, and other clarifications above. Finally, the modifications distinguish secondary outcomes from exploratory outcomes with an asterisk.

Modification #6 (Date: 3/20/2018)

Original protocol: The protocol was inconsistent regarding reporting of overdoses to the DSMB.

Modification: We plan to measure ODs and will report those data to the DSMB for tracking purposes.

Rationale: This modification is only to clarify the protocol regarding reporting overdoses (ODs) since this was not listed in all places.

Modification #7 (Date: 3/20/2018)

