Prescribing providers (Adoption)	Number and % of PC providers who order buprenorphine or injectable naltrexone for at least 2 patients with OUDs
OUD treatment starts per week (Implementation fidelity)	Mean number of patients initiating buprenorphine or injectable naltrexone per week over the 2 years post randomization
Time to OUD treatment (Implementation fidelity)	Median number of days (0 days if same day to infinity if untreated) from first visit with a new OUD ICD diagnosis (no prior diagnosis) to OUD treatment initiation during follow-up
Urine drug monitoring (Implementation fidelity)	Median frequency of urine drug testing in the 1 and 3 months post initiation of OUD medication treatment. (Note: Although this aspect of the MA Model is specified locally because there is no scientific consensus on the optimal algorithm, urine monitoring early in treatment is recommended)
Re-initiation of OUD treatment (Implementation fidelity)	Proportion of patients with prior EHR documentation of OUD treatment followed by at least a 3-month gap in treatment, who re-initiate buprenorphine or injectable naltrexone
Methadone OTP	Proportion of patients who are receiving methadone maintenance (restricted to 3 sites with OTP data)
Buprenorphine dose	Highest mean daily buprenorphine dose in any month of buprenorphine treatment (patient-level measure)
Additional Patient Outcome Measures	
Urgent care or ED use (Secondary patient outcome)	Number of visits to urgent care or EDs during follow-up among patients with an OUD diagnosis
Inpatient Days hospitalized (Secondary patient outcome)	Number of days hospitalized during follow-up, among patients with an OUD diagnosis
Opioid overdose (Secondary patient outcome)	Proportion of patients with an ICD code for opioid overdose during follow-up (Note this is expected to be biased due to improved ascertainment in the PROUD clinics due to NCM follow-up with patients with OUDs).
HCV viral cure (Secondary patient outcome)	Number of patients with HCV who have documented viral suppression among all with diagnosed chronic active HCV.

Additional Outcome Measures - Other Processes of Care	
New diagnosis or treatment of other substance use condition	Number of patients who have a new diagnosis or treatment for another substance use condition (not diagnosed prior 2 years)
New diagnosis or treatment of mental health conditions	Number of patients who have a new diagnosis or treatment for a mental health condition (not diagnosed prior 2 years)

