#### **4.2 Definition of Objective 2 Effectiveness Outcome Measure (Powered Secondary Outcome)**

The primary effectiveness (Objective 2) endpoint is a person-level count measure of the number of days of acute care utilization in the follow-up period, among patients with an OUD diagnosis pre-randomization. This measure includes visits to urgent care clinics or emergency departments (EDs), as well as days hospitalized. Acute care utilization will be determined from the EMR and insurance claims data when available.

For hospitalizations, the number of inpatient days will be the number of days from admission to discharge, inclusive. For urgent care or ED (referred to collectively as “emergency care”), each unique date with a visit to an urgent care or ED will be counted as 1 day (even if the patient stays overnight), except in the uncommon event that an ED visit spanned 3 or more days ( $< 0.5\%$  of ED records collected in Data Pull 4, including both randomized and non-recruited UPC clinics), in which case the encounter will be classified as a hospitalization (as patients may be boarded in an ED until a hospital bed becomes available and some are subsequently discharged from the ED if no hospital bed ever became available). If a patient is admitted from urgent care or an ED, the ED or urgent care day is not (double) counted when counting the number of days of acute care.

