### 4.3 Definitions of Secondary Measures

Additional secondary measures will be analyzed to describe outcome measures reflecting processes of care, implementation, and effectiveness. The following table describes each of the measures that will be examined either descriptively, or through formal modeling, as described in the statistical analysis section below. Measures will be calculated broadly in the full study sample to facilitate analyses across different study samples. For example, we will calculate the number of days of OUD medication treatment for each patient, which will be summed across patients as part of the primary Objective 1 outcome and will also be analyzed at a patient-level among patients with an OUD diagnosis pre-randomization. Other implementation measures (e.g., number of patients treated) will be analyzed in both the full study sample of all patients with a visit, as well as in the subsample of these patients who had an OUD diagnosis pre-randomization.

**Table 2: Primary, Secondary, and Other Outcomes Measured During Post-Randomization Period Based on EHR Data (\*measures from clinicaltrials.gov)**

Outcome Measures

*Objective 1. Patient-days of OUD medication treatment (primary outcome). Clinic-level number of patient-days of OUD treatment with buprenorphine and XR-NTX documented in the EHR during the period from randomization until two years after, reported per 10,000 PC patients in the clinic in the two years post-randomization.

*Objective 2. Acute care utilization (secondary outcome). Patient-level number of days of acute care utilization during the period from randomization until two years after, among patients with an OUD diagnosis documented in the EHR in the three years prior to randomization.

Other Outcome Measures of Implementation

*Newly diagnosed OUD (Implementation Reach). Clinic-level number of patients with a new International Classification of Disease (ICD) code for OUD documented in the EHR during the period from randomization until two years after who did not have an OUD diagnosis documented in the EHR in the three years prior to randomization, reported per 10,000 patients in the PC clinic in the two years post-randomization.
 
This measure will also be estimated for any OUD diagnosis (new and previous diagnoses).

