d Days hospitalized also includes emergency department or urgent care visits that resulted in a hospitalization. [Report % of hospitalizations that started in (or immediately preceded) an emergency visit.] Specific cut-points for categorization to be determined based on empirical distribution at baseline

e Emergency care includes visits to an emergency department or urgent care facility that did not result in hospitalization; specific cut points for categorization to be determined based on empirical distribution at baseline

**Table 4.** Observational analysis of effect of PROUD Intervention on OUD treatment in the larger secondary sample that includes patients with newly recognized OUD in trial clinics post-randomization

Measure	Pre-randomization Sample: Patients in Trial Clinics with Documented OUD Pre- randomization a		Post-randomization Sample: Patients New to Trial Clinics or with Newly Documented OUD Post-randomization				Secondary Sample (Overall)
	Treatment effect b	95% CI	Intervention	Usual Care	Treatment effect b	95% CI	Omnibus P value c

Same measures as Table 2

a Estimating the same thing as Table 2, but adjusted for demographics and not adjusting for baseline (which is not measured among patients new to the health system post-randomization); likely will be omitted from main paper (include in supplement instead)

b Estimated from a mixed-effect model with clinic-specific random intercept and an interaction term between the intervention effect and the timing of when the patient was first seen in the trial clinic with diagnosed OUD (pre- or post-randomization) and adjusted for demographics

c Testing for whether there is a difference between intervention and usual care clinics for either subset of patients (primary sample or secondary sub-sample added to the primary sample)

**Table 5.** Observational analysis of intervention effect on acute care utilization in the larger secondary sample including patients with newly recognized OUD in trial clinics post-randomization

Measure	Pre-randomization Sample: Patients in Trial Clinics with Documented OUD Pre- randomization a		Post-randomization Sample: Patients New to Trial Clinics or with Newly Documented OUD Post-randomization		Secondary Sample (Overall)		

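### The urgent care/ED use outcome counts only visits that did not end in admission, so its rate ratio mixes ED use with any change in the admission share

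*SAP*

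**What the plan says.** SAP Section 4.3, Table 2 defines the outcome as "Patient-level number of visits to urgent care or EDs during the period from randomization until two years after" among patients with OUD documented before randomization. The asterisk on it marks "measures from clinicaltrials.gov". A note in the same cell then says "ED or Urgent Care visits that lead to hospitalization are classified as inpatient".

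The shells in SAP Section 10.2 carry the restriction into reporting. Table 3, note e: "Emergency care includes visits to an emergency department or urgent care facility that did not result in hospitalization". That note applies both to the row for days of emergency care and to the visit categories (Never, Once, 2-3 times, 4+ times).

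The protocol wording has no such restriction. Table 7 in Section 8.2 has "Number of visits to urgent care or EDs during follow-up among patients with an OUD diagnosis". Modification #5 rewords the entry, again without excluding admitted visits, and explains: "We are updating additional outcome measures in Table 7 to align with our published ClinicalTrials.gov registration".

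For the composite of acute-care days, SAP Section 4.2 has a rule against double counting: "If a patient is admitted from urgent care or an ED, the ED or urgent care day is not (double) counted". There the admitted visit is still represented, because "the number of inpatient days will be the number of days from admission to discharge, inclusive".

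**The concern.** The no-double-count rule is needed when ED days and hospital days are summed. A stand-alone ED and urgent-care outcome has nothing to double count. Applied there, the rule makes the count depend on the decision to admit, which happens after randomization and which the intervention may change. Protocol Section 3.2.3.2 hypothesizes fewer urgent-care and ED visits as such, alongside fewer days in hospital, so ED attendance is a question of its own.

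At stake is the reading of this secondary outcome. Its rate ratio can move because attendance changed, because disposition changed, or both, and no planned analysis separates the two. The category row has a plainer problem: a patient whose ED visits all ended in admission would be reported as never having had an emergency care visit.

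**Working it through.** The plan gives no rate, power or admission share for this outcome, so there is no figure to reproduce. The check is an identity followed by assumed values.

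**Inputs.** V = all ED and urgent-care visits per patient; a = share of them ending in admission (a1 under PROUD, a0 under usual care). Neither a1 nor a0 is in the documents, so every share below is an assumption. Under SAP Section 5.6 the outcome is analysed as for Objective 2, giving a rate ratio adjusted for the baseline value of the same measure.

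**Identity.** Scored count = V × (1 − a). Hence

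RR_scored = RR_visits × (1 − a1)/(1 − a0).

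The scored ratio exceeds 1 only if RR_visits > (1 − a0)/(1 − a1).

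| a0 to a1 (assumed) | RR_scored, visits unchanged | Break-even RR_visits | RR_scored if visits truly fall 10% |
|---|---|---|---|
| 20% to 19% | 0.81/0.80 = 1.01 | 0.80/0.81 = 0.99 | 0.90 × 1.0125 = 0.91 |
| 20% to 15% | 0.85/0.80 = 1.06 | 0.80/0.85 = 0.94 | 0.90 × 1.0625 = 0.96 |
| 30% to 20% | 0.80/0.70 = 1.14 | 0.70/0.80 = 0.88 | 0.90 × 1.143 = 1.03 |
| 30% to 15% | 0.85/0.70 = 1.21 | 0.70/0.85 = 0.82 | 0.90 × 1.214 = 1.09 |
| 20% to 25% | 0.75/0.80 = 0.94 | 0.80/0.75 = 1.07 | 0.90 × 0.9375 = 0.84 |

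The first two rows attenuate a true 10% fall, the next two reverse its sign, and the last exaggerates it. With 30% to 15% and a larger true fall (RR_visits 0.65), the scored ratio is 0.65 × 1.214 = 0.79: right direction, attenuated.

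**Baseline adjustment.** It does not remove the factor. The baseline covariate uses the same definition and cannot carry a change in the admission share that occurs after randomization.

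**Composite, for contrast.** Take 4.0 visits over two years (the Phase 1 acute-care figure in SAP Section 6.2.1, used here only as an illustrative V), an assumed 4-day stay, unchanged visits and 30% to 15%.
- Usual care: 4 × 0.70 = 2.8 released visits plus 4 × 0.30 × 4 = 4.8 inpatient days = 7.6 days.
- PROUD: 4 × 0.85 = 3.4 plus 4 × 0.15 × 4 = 2.4, giving 5.8 days.
- Composite ratio 5.8/7.6 = 0.76; treat-and-release ratio 3.4/2.8 = 1.21; all-visit ratio 4.0/4.0 = 1.00.

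The composite moves the right way while the treat-and-release row shows an increase with no extra visit.

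**Unit.** Table 2 says visits. The Table 3 row is in days, and SAP Section 4.2 counts each unique date once, so two visits on one date become one.

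**The case against.** The rule is disclosed in Table 2 and in the shells, and it splits the composite into parts that do not overlap, which helps explain it. Admitted visits are reclassified rather than lost: they enter inpatient days, number of hospitalizations, any acute care and the composite. Read together, the Table 3 rows would show fewer hospital days beside more treat-and-release care, which is what happened in that scenario. The shell notes also ask for the percentage of hospitalizations that began with an emergency visit, so a shift in disposition could be noticed. Protocol Section 8.3.2 leaves outcome definitions to the SAP. The shares are assumed, and a ratio of 1.06 is small when even the composite reaches 80% power only below 0.65 under the primary assumption (SAP Section 6.2.2). Secondary outcomes are in any case to be interpreted with caution (protocol Section 11.5).

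Most of this stands and limits the point to an inexpensive improvement in one secondary outcome. It does not make the row answer whether ED use changed. The planned percentage is descriptive and has hospitalizations as its denominator; with hospital days and categories beside it, it does not recover the all-visit count or an adjusted ratio. Additivity is a reason to keep the treat-and-release row under an accurate label, not to let it stand in for ED use.

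A reader might infer that the SAP breaches the registration. The documents do not show that: the registry record is not among them, the protocol's short wording is silent on admitted visits, and definitions were delegated to the SAP. What they show is a narrowing of the protocol's wording.

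**Conclusion.** The concern holds in conditional form. As defined, the outcome measures treat-and-release visits, and its rate ratio is the true visit ratio multiplied by (1 − a1)/(1 − a0). With equal attendance, assumed shares of 20% to 19%, 20% to 15% and 30% to 20% give 1.01, 1.06 and 1.14. These sizes rest wholly on assumed shares, since the documents give none.

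It would be tempting to say that an intervention which makes visits less severe will be scored as increasing ED use. That needs two things together: a lower admission share, and a fall in visits too small to offset it. The protocol expects visits to fall as well, and a large enough fall leaves only attenuation. It would also be wrong to conclude that the main Objective 2 result is biased. The composite applies its rule where it belongs and is not affected.

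**What to change.** - For this outcome, count all ED and urgent-care visits regardless of disposition, as visits. Apply this to the modelled count and to the Never/Once/2-3/4+ categories, and change the Table 2 note and Table 3 note e accordingly, with the matching baseline note in Table 1.
- Keep the no-double-count rule for the composite.
- Keep the present measure as an additional row labelled 'treat-and-release emergency care days'.
- Report the share of ED and urgent-care visits ending in admission, by arm.

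The cost is a revised note and one derived variable. No new data are needed, because the shells already require hospitalizations that began with an emergency visit to be identified. The downside is that the all-visit row and hospital days no longer add up to the composite; the retained treat-and-release row preserves that decomposition for readers who want it.

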## 5.0 ANALYSES OF OUTCOME MEASURES

### 5.1 Primary Analytic Method for Primary Implementation Outcome Measure

Since randomization and the intervention occur at the clinic-level, the unit of analysis will be clinic and not patient for the primary outcome. The mixed effects model evaluating the effect of the PROUD intervention is:

$$y_{ij} = \alpha + \beta * trt_{ij} + \gamma * z_{ij} + \theta_j + \epsilon_{ij} \quad (1)$$

where

- 1)  $y_{ij}$  is the observed value of the primary outcome measure for clinic  $i$  at health care system (HCS)  $j$
- 2)  $trt_{ij}$  is the treatment indicator (PROUD intervention) for clinic  $i$  at HCS  $j$
- 3)  $z_{ij}$  is the observed value of the primary outcome measure for the two years prior to randomization (hereafter baseline) for clinic  $i$  at HCS  $j$
- 4)  $\theta_j$  is the random effect for HCS  $j$  and is distributed  $N(0, \sigma_{\theta}^2)$
- 5)  $\epsilon_{ij}$  is the error term for clinic  $i$  at HCS  $j$  and is distributed  $N(0, \sigma_{\epsilon}^2)$

Our primary hypothesis is that there will be a significant increase in the number of patient days of medication treatment for OUDs during the follow-up period in clinics randomized to the PROUD intervention as compared to clinics randomized to UPC. To evaluate this hypothesis, analyses test whether  $\beta$  (PROUD intervention effect) significantly exceeds zero using a one-sided hypothesis test at the 0.05 level. This is appropriate because our primary aim is to test superiority of implementation of the MA model relative to Usual PC in order to inform health systems' decisions as to whether to implement this model of OUD care.

Example SAS code for the analysis is as follows:

```
proc mixed data = primout;
  class arm;
  model scaletotdays = arm basevalue / solution;
  random intercept / subject = site;
  estimate "Treatment Effect" arm 1 -1;
run;
```

where "arm" is the treatment assignment ( $trt_{ij}$ ), "scaletotdays" is the value of the primary outcome measure ( $y_{ij}$ ), "basevalue" is the value of the primary outcome measure for the two years prior to randomization ( $z_{ij}$ ) and "site" indexes the different HCSs ( $j$ ).

This model allows for clinics to be correlated within a HCS, in addition to allowing for an association of the scaled days of OUD treatment prior to randomization with the post-randomization outcome.

